### **10.2. Treatment of Overdose**

GSK does not recommend specific treatment for an overdose. The investigator will use clinical judgement to treat an overdose as and when they are made aware of this.

In the event of an overdose, the investigator should:

1. Contact the Medical Monitor immediately.
2. Closely monitor the participant for AE/SAE and laboratory abnormalities until GSK2983559 can no longer be detected systemically (at least 48hours).
3. Obtain a plasma sample for PK analysis if requested by the Medical Monitor (determined on a case-by-case basis).
4. Document the quantity of the excess dose as well as the duration of the overdosing in the CRF.

Decisions regarding dose interruptions or modifications will be made by the investigator in consultation with the Medical Monitor based on the clinical evaluation of the participant.

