### **5.4. Scientific Rationale for Study Design**

The current study described herein has been designed to address regulatory guidance for FTIH studies and in particular General Considerations for Clinical Trials [The International Council for Harmonisation of Technical Requirements for Pharmaceuticals for Human Use (ICH) E8/ Committee For Proprietary Medicinal Products (CPMP)/ICH/291/95] and Guideline on Strategies to Identify and Mitigate Risk for First-in-Human Clinical Trials with Investigational Medical Products [EMA/CHMP/SWP/28367/07] as well as pre-clinical findings for GSK2983559, contributing to the frequency, type and duration of safety assessment and monitoring during treatment periods during each cohort.

The sequential design of the single dose components (Part A) and estimated 5-hour half-life ( $t_{1/2}$ ) will allow for dose escalation to occur after less than 6 days of washout. The predicted time for GSK2668176 plasma concentrations to reach the lower limit of quantification (LLOQ, 0.20 ng/ml) after dosing for the highest selected dose (see Section 5.5 below) was 3 days. This will allow any adjustment needed based on emerging safety, tolerability, and PK information. The randomised crossover design was chosen to allow for treatment comparison between and within participants. Further, a food-effect evaluation is planned to support progression into patient studies.

In Part B, the 14-day dosing will provide exposure to PK steady state and will also be informative of the likely safety and tolerability in future longer studies.

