## **5.5. Dose Justification**

### **5.5.1. Human PK prediction**

GSK2983559 is a phosphate ester pro-drug which is converted into GSK2668176 (active moiety) primarily by the alkaline phosphatase present in the intestinal lumen. The systemic exposure of the prodrug GSK2983559 is predicted to be <2% in humans and is considered to have a negligible contribution to clinical effect and is not considered relevant for human dose determination.

The human pharmacokinetic (PK) profiles as well as parameters of parent drug GSK2668176 following oral dosing of prodrug GSK2983559 were predicted using in vitro to in vivo extrapolation and allometric scaling. The predicted human mean absorption rate constant (0.85 1/h), clearance (0.426 L/h/Kg), volume of distribution (2.8 L/Kg), half-life (4.6 hours) and bioavailability (70%) were used to determine the blood PK profiles for GSK2668176 following oral administration of GSK2983559.

As the exposures observed in preclinical species were in plasma, the predicted human PK estimates in blood were multiplied by a factor of 0.83 (blood/plasma ratio=1.2 for GSK2668176) to give the corresponding human PK estimates in plasma for calculating the safety fold coverage to the no observable adverse effect limit (NOAEL).

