### Dose selection for Part B

Part B (repeat dose) of the study will be initiated after completion of Part A. Dose selection will be based upon consideration of available safety, tolerability and PK data from Part A and/or preceding repeat dose cohorts in Part B. Based on the observed half-life of approximately 8 h GSK2668176 in humans, minimum accumulation is anticipated after BID dosing. The dose of GSK2983559, noted as X, is anticipated to provide 90% inhibition at Ctrough levels of GSK2668176 in 50% of the population and will be re-estimated based on the PK and PD data collected in the early doses in Part A. The initial

dose in Part B (Cohort 3, repeat dose) will be approximately half X. Dose escalation in the repeat dose part of the study will not exceed 2-fold between cohorts and will be driven by safety and PK stopping criteria (see Section 8). In addition, a dose will not be assessed as a repeat dose until the anticipated steady-state exposure ( $C_{max}$  and  $AUC_{(0-\tau)}$  on Day 14) for that dose have been evaluated and shown not to have met safety stopping criteria in the single dose portion of the study (Part A). Based on current PK predictions a dose of 200 mg BID dosing regimen is predicted to provide 90% inhibition in approximately 90% of subjects. Dose levels higher than this may be explored in order to evaluate dose response in future phase 2 dose ranging study provided that exposure levels for that dose has been previously evaluated in Part A of the study.

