## 8. DOSE ESCALATION CRITERIA

### 8.1. PK criteria for GSK2668176

Due to the non-tolerated high dose of 420 mg/kg/day GSK2983559 in minipigs, the PK stopping criteria are based on  $AUC_{(0-24)}$  and  $C_{max}$  values at 1/3rd of the NOAEL of 120 mg/kg/day GSK2983559 (GSK2668176  $AUC_{(0-24)}$  50.9  $\mu\text{g}\cdot\text{h}/\text{mL}$ ,  $C_{max}$  7.5  $\mu\text{g}/\text{mL}$ ).

The decision to proceed to the next dose level of GSK2983559 in each part of this study will be made by the DEC, based on safety, tolerability, and preliminary PK data obtained (through at least 24 hours post dose) with at least 4 participants having received active treatment (GSK2983559) at the current dose level. The actual doses to be administered may be adjusted based on safety, tolerability and preliminary PK data at previous dose levels; these dose adjustments may involve either an increase or a decrease in the planned dose, but will not exceed PK criteria. Planned doses may also be repeated.

It is planned that the predicted human mean GSK2668176  $AUC_{(0-24)}$  or  $C_{max}$  values **will not** exceed the mean GSK2668176  $AUC_{(0-24)}$  and  $C_{max}$  values observed at one third of the NOAEL in minipig (16.94  $\mu\text{g}\cdot\text{h}/\text{mL}$  and 2.5  $\mu\text{g}/\text{mL}$ , respectively). In addition, the predicted human maximum  $AUC_{(0-24)}$  or  $C_{max}$  values **will not** exceed the maximum observed  $AUC_{(0-24)}$  and  $C_{max}$  values at one third NOAEL (21.6  $\mu\text{g}\cdot\text{h}/\text{mL}$  and 3.25  $\mu\text{g}/\text{mL}$ ).

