### 11.3.4. Interim Analyses

Dose escalation meetings will occur after each period in Part A and after the completion of 14 days dosing of each cohort in Part B. The decision to proceed to the next cohort and next dose strength to be studied, will be made by DEC based on assessment of safety (e.g., AEs, clinical laboratory results, vital signs and ECG) and plasma GSK2983559 pharmacokinetic and 5-ABT concentrations obtained in all participants at the prior dose level. Individual safety data (adverse events, laboratory safety tests, ECGs and vital

signs) will be reviewed. This study is double blind (sponsor open), where the participant, investigator and site staff will remain blinded to the treatment allocation. Sponsor open refers only to those members of the DEC.

Following completion of Cohort 1 (Part A) and before starting Cohort 2 (Part A), a GSK internal safety board (independent of DEC) will be reviewing the data.

A formal interim analysis may be performed during the study on completed cohorts in Part A of the study to aid internal decision making only. Only the DEC members will be unblinded. There will be no changes to the study design or planned number of participants in future cohorts as a result of this interim analysis. This analysis may include review of individual participant data, summaries, graphical presentations and/or statistical analysis.

The Reporting and Analysis Plan will describe the planned interim analysis in greater detail.

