### **3. PLANNED ANALYSES**

#### **3.1. Interim Analyses**

Dose escalation meetings occurred after each period in Part A and were scheduled to occur following the completion of 14 days dosing of each cohort in Part B. The decision to proceed to the next cohort and next dose strength to be studied, was made by the Dose Escalation Committee (DEC) based on assessment of blinded safety (e.g., AEs, clinical laboratory results, vital signs and ECG), active moiety (GSK2668176) pharmacokinetic and 5-ABT concentrations obtained in all participants at the prior dose level. Individual safety data (adverse events, laboratory safety tests, ECGs and vital signs) was reviewed. This study was double blind (sponsor open), where the participant, investigator and site staff will remain blinded to the treatment allocation. Sponsor open refers only to those members of the DEC as required.

Following completion of Cohort 1: Part A and before starting Cohort 2: Part A, a GSK internal safety board (independent of DEC) reviewed the emerging PK and safety data.

A formal interim analysis was due to be performed during the study on completed cohorts in Part A of the study to aid internal decision making only. The study was terminated prior to completion of Part A.

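### Section 10.2 ends close overdose monitoring on detection of the prodrug GSK2983559 with a 48-hour floor, which does not fit the protocol's own account of how long the active moiety GSK2668176 stays measurable at higher doses

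*Protocol*

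**What the plan says.** Section 10.2 tells the investigator to monitor closely for adverse events and laboratory abnormalities after an overdose "until GSK2983559 can no longer be detected systemically (at least 48hours"). The bracket is a floor, so the period lasts until detection ends and for no less than 48 hours. A plasma PK sample is taken only if the Medical Monitor asks for one.

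Elsewhere the protocol treats prodrug and active moiety as separate compounds:

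- Section 3.2 says GSK2983559 is quickly broken down to GSK2668176, the RIP2 kinase inhibitor.
- Section 5.5.1: "The systemic exposure of the prodrug GSK2983559 is predicted to be <2% in humans". It adds that the contribution to clinical effect is negligible and that the prodrug does not matter for choosing the human dose.
- Section 8.1 is headed "PK criteria for GSK2668176" and puts every exposure ceiling on that compound.
- Section 5.4 gives the predicted time for GSK2668176 to fall to 0.20 ng/mL: "after dosing for the highest selected dose (see Section 5.5 below) was 3 days". The same paragraph uses an estimated half-life of 5 hours.
- Dose selection for Part B (Section 5.5.4): "Based on the observed half-life of approximately 8 h GSK2668176 in humans".

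Section 11.3.4 says escalation rests on safety and "plasma GSK2983559 pharmacokinetic and 5-ABT concentrations obtained in all participants at the prior dose level". SAP Section 3.1 has nearly the same sentence but names "active moiety (GSK2668176) pharmacokinetic and 5-ABT concentrations".

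**The concern.** A rule that ends when a compound is no longer detected depends on which compound is named. Section 10.2 names the one the protocol expects to be almost absent from the circulation. That leaves the 48-hour floor to do the work, and the floor is shorter than the protocol's own 3-day prediction for GSK2668176 after the highest planned dose. The prediction also predates the longer half-life seen in Cohort 1.

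What is at stake is whether a safety instruction means what its authors intended. A site that follows it to the letter could end close monitoring with the active moiety still measurable. Section 11.3.4 contains a similar naming slip, with less attached to it.

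**Working it through.** **Without any modelling.** Section 5.4 predicts 3 days (72 h) at the highest dose, and the floor in Section 10.2 is 48 h. On the protocol's own figures GSK2668176 outlasts the floor by about a day.

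**Reproducing the 3 days.** Inputs from Section 5.5.1: ka = 0.85/h, CL = 0.426 L/h/kg, V = 2.8 L/kg, F = 0.70, blood-to-plasma factor 0.83. Then ke = 0.426/2.8 = 0.152/h, a half-life of 4.56 h. Two assumptions are not in the documents: body weight W of 60 to 80 kg, and a GSK2668176-to-prodrug mass ratio r of 0.8 to 1.0. The one-compartment oral model in ng/mL is

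C(t) = 830 · F · r · D / (W · V) · ka/(ka − ke) · (e^(−ke·t) − e^(−ka·t)).

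- Check at 2 mg (70 kg, r = 1): Cmax 4.07 ng/mL and AUC 0.039 µg.h/mL. Section 5.5.2 states 0.004 µg/mL and 0.038 µg.h/mL.
- 600 mg (70 kg, r = 1): the late-phase intercept is 830 × 0.70 × 600/(70 × 2.8) × 0.85/0.698 ≈ 2,166 ng/mL. Time to 0.20 ng/mL = ln(2,166/0.20)/0.152 ≈ 61 h, or 2.54 days.
- Over the assumed ranges: 2.45 to 2.59 days at 600 mg and 2.53 to 2.67 days at 800 mg (the original top dose in Section 7.3). With the 5 h half-life of Section 5.4, 2.68 to 2.92 days across both doses.

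So 3 days is a fair rounding of the pre-study parameters.

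**With the observed half-life of 8 h, two routes at 600 mg.**

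1. From the Table 7 Cmax of 1.836 µg/mL (1,836 ng/mL), log-linear decline from dosing. Half-lives to 0.20 ng/mL = log2(1,836/0.20) = 13.16, and 13.16 × 8 h = 105 h (4.4 days). At 48 h: 1,836/2^6 = 28.7 ng/mL, which is 143 times 0.20.
2. From the Table 7 trough inhibition at 100 mg (73%). With a Hill slope of 1 (assumed), IC50 = 86.67/9 = 9.63 ng/mL, so the 24 h level is 9.63 × 0.73/0.27 = 26.0 ng/mL, and × 6 gives 156 ng/mL at 600 mg. At 48 h: 156/2^3 = 19.5 ng/mL, about 98 times 0.20. Time to 0.20 = 24 + 8 × log2(156/0.20) = 101 h (4.2 days). The same IC50 and scaling return Table 7's 84%, 92% and 94% at 200, 400 and 600 mg.

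The compartment model with the half-life set to 8 h gives 4.25 to 4.50 days at 600 mg.

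**Other doses, route 1, 8 h half-life.**

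| Dose (mg) | Table 7 Cmax (ng/mL) | At 48 h (ng/mL) | Time to 0.20 ng/mL |
|---|---|---|---|
| 2 | 10.5 | 0.16 | 46 h (1.9 days) |
| 100 | 306 | 4.8 | 85 h (3.5 days) |
| 400 | 1,224 | 19.1 | 101 h (4.2 days) |
| 600 | 1,836 | 28.7 | 105 h (4.4 days) |

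Under linear kinetics each doubling of dose adds one half-life, 8 h. At 2 mg the floor is sufficient; at 100 mg and above it is not.

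**The case against.** **Loose naming.** GSK2983559 is also the protocol's name for the study drug, as in its references to the last dose, so 10.2 could mean the drug and whatever circulates from it. That is possible, and it makes the instruction ambiguous rather than plainly wrong. But Section 10.4 assays the two compounds separately, so detection has a specific analytical meaning that the reader has to guess.

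**Participants left unobserved.** A reader might infer that a participant goes unwatched after 48 h. The documents do not support that. Section 10.2 requires immediate contact with the Medical Monitor. Section 10.1.1 collects adverse events to the follow-up visit, which Section 5.1 places at least 7 days after the last dose, beyond the 105 h above. Only close monitoring could end early. Nor do the documents show that the prodrug is undetectable at 48 h: they give neither its quantification limit nor its observed half-life, and the amendment rationale reports Cmax and AUC for it.

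**Harmful or active levels at 48 h.** This too is tempting. The inhibition implied by 20 to 29 ng/mL depends on the assumed Hill slope and an ex vivo assay, and Section 5.5.3 says the inhibition needed for efficacy is unknown. Against the Section 8.1 mean Cmax ceiling of 2.5 µg/mL, 28.7 ng/mL is about 1% (28.7/2,500). The 600 mg figures also describe a planned dose, after which Section 5.1 already discharges participants following the 48-hour assessments. Measurable drug at 48 h is therefore not peculiar to overdose.

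**Wrong analyte used for escalation.** Section 11.3.4 might suggest that the committee reviewed data it could not compare with the ceilings. It did not have to. Section 8.1 sets numeric limits on GSK2668176, Appendix 3 requires all available PK data and strict application of Section 8, Section 10.4.1 covers both analytes in the PK samples, and SAP 3.1 reports that the active moiety was used.

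What stands is the mismatch between the end point in 10.2 and Sections 3.2, 5.4, 5.5 and 8.1.

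**Conclusion.** The point holds as an inconsistency in an operative safety instruction. Read literally, the detection criterion and the floor in Section 10.2 can both be satisfied while GSK2668176 is still measurable after the higher doses. The conflict with Section 5.4 (3 days against 48 hours) needs no assumptions.

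The updated size, about 4.2 to 4.4 days at 600 mg, assumes an 8 h half-life throughout the decline, exposure linear in dose from 100 mg, and standard-capsule data carried over to the enteric capsule. Inter-individual spread is not modelled. The 600 mg dose was never reached: SAP Sections 2.1 and 5.1 show that the study stopped in Cohort 2 with 200 and 400 mg the only enteric doses used. The 400 mg row is therefore the relevant one for what was actually given.

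No endpoint or planned analysis is affected. The Section 11.3.4 wording is minor, and no effect on any escalation decision is shown. Nothing here establishes what the monitoring period should be.

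**What to change.** - Reconcile Section 10.2 with Sections 3.2, 5.4, 5.5.1, 8.1 and the Part B dose-selection text. State which analyte is meant by no longer detected, and whether the 48-hour floor is consistent with the observed half-life. The monitoring rule is for the sponsor to set.
- Update the 3-day prediction in Section 5.4 to the observed half-life, with the dose it refers to.
- Align the analyte named in Section 11.3.4 with Section 8.1 and SAP 3.1.

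The cost is wording in three protocol sections. No new assay is needed, because Section 10.4.1 already covers GSK2668176. With the study terminated, the practical value is an accurate record and not carrying the text into a later protocol for this compound.

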### **10.3. Safety Assessments**

Planned time points for all safety assessments are provided in the SoA.

#### **10.3.1. Physical Examinations**

- A full physical examination will include, at a minimum, assessments of the Skin, Cardiovascular, Respiratory, and Gastrointestinal systems. Height and weight will also be measured and recorded.
- A brief physical examination will include, at a minimum, assessments of the skin, lungs, cardiovascular system, and abdomen (liver and spleen).
- Investigators should pay special attention to clinical signs related to previous serious illnesses.

#### **10.3.2. Neurological Exams**

Neurological examination will include, at a minimum, assessment of: mental status, gait, balance, coordination, cranial nerves, motor power, reflexes, and sensory system (light

touch and pain). Assessments will be standardized across all scheduled time points (see SoA). Significant changes from the baseline or any clinically significant changes will be noted as part of further scheduled examinations or unscheduled examinations (if needed).

Clinically significant abnormalities or changes in status from baseline will be:

- entered as an adverse event,
- may trigger increased monitoring of the subject(s),
- may result in withdrawal of the subject (see Section 9.2),
- may result in referral to a specialist.

### 10.3.3. Vital Signs

- Vital signs will be measured in a semi-supine position after 5 minutes rest in a quiet setting without distractions (e.g., television, cell phones) and will include temperature, systolic and diastolic blood pressure, and pulse and respiratory rate.
- In Part A and Part B on Day 1 vital signs (to be taken before blood collection for laboratory tests) will consist of triplicate pulse and blood pressure measurements only (3 consecutive blood pressure readings will be recorded at intervals of at least 1 minute). All 3 readings will be recorded on the CRF.

### 10.3.4. Electrocardiograms

- Triplicate OR Single 12-lead ECG will be obtained as outlined in the SoA using an ECG machine that automatically calculates the heart rate and measures PR, QRS, QT, and QTc intervals. Refer to Section 9.4 for QTc withdrawal criteria and additional QTc readings that may be necessary.
- At each time point at which triplicate ECG are required, 3 individual ECG tracings should be obtained as closely as possible in succession, but no more than 2 minutes apart. The full set of triplicates should be completed in less than 4 minutes.
- Continuous cardiac telemetry will be performed at time points indicated in the SoA (Section 2). Full disclosures will be reviewed in detail and the review maintained as part of the subject's source documents.
- Holter monitoring will be performed at screening only. This 24-hour Holter will be performed to eliminate participants with non-clinically overt cardiac arrhythmias.

### 10.3.5. Clinical Safety Laboratory Assessments

- Refer to [Appendix 2](#) for the list of clinical laboratory tests to be performed and to the SoA for the timing and frequency.
- The investigator must review the laboratory report, document this review, and record any clinically relevant changes occurring during the study in the AE

section of the CRF. The laboratory reports must be filed with the source documents. Clinically significant abnormal laboratory findings are those which are not associated with the underlying disease, unless judged by the investigator to be more severe than expected for the participant's condition.

- All laboratory tests with values considered clinically significantly abnormal during participation in the study should be repeated until the values return to normal or baseline or are no longer considered significantly abnormal by the investigator or medical monitor.
- If such values do not return to normal/baseline within a period of time judged reasonable by the investigator, the etiology should be identified and the sponsor notified.
- All protocol-required laboratory assessments, as defined in [Appendix 2](#), must be conducted in accordance with the laboratory manual and the SoA.

## **10.4. Pharmacokinetics**

### **10.4.1. Blood Sample Collection**

Blood will be collected into ethylenediaminetetraacetic acid (EDTA) tubes and processed to plasma for PK analysis of GSK2983559, GSK2668176, 5ABT and NAc-5ABT at the time points indicated in Section 2, SoA Tables. The actual date and time (24-hour clock time) of each blood sample collection will be recorded. The timing of PK samples may be altered and/or PK samples may be obtained at additional time points to ensure thorough PK monitoring.

In Part B on Day 1 and Day 14, at each sampling time point an additional blood sample will be collected for metabolite profiling.

Details of blood sample collection, processing, storage and shipping procedures are provided in the SRM.

### **10.4.2. Plasma Sample Analysis**

Plasma analysis will be performed at a bioanalytical site (to be detailed in the SRM) under the control of Platform Technology and Science In Vitro/In Vivo Translation (PTS IVIVT) and Third Party Resource, GlaxoSmithKline. Concentrations of GSK2983559, GSK2668176, 5ABT and NAc-5ABT in plasma samples will be determined using the currently approved bioanalytical methodology. Raw data will be archived at the bioanalytical site (detailed in the SRM).

Once the plasma sample has been analysed for GSK2983559, GSK2668176, 5ABT and NAc-5ABT, any remaining plasma sample may be analysed for other compound-related material and the results may be reported under a separate PTS-Global Spectroscopy, GlaxoSmithKline protocol.

Drug concentration information that may unblind the study will not be reported to investigative sites or blinded personnel until the study has been unblinded.

